The specific objective of this study is to generate evidence in support of the feasibility of our developed methods for the evaluation of 1) relative contribution of lower back tissues to spinal loads, and 2) the resultant spinal loads experienced during daily activities **in veterans with non-specific LBP**. Results of this feasibility study will enable proper design of our future projects, wherein we will investigate the role of spinal loads experienced in daily life activities in clinical presentation of LBP. We have developed several innovative computational and experimental methods for a comprehensive and personalized assessment of spinal loads. Specifically, the relative mechanical contribution of active and passive lower back tissues to spinal loads is assessed using advanced measures of [bulk] lower back mechanical behavior (MB), whereas muscular responses to physical demands of daily activities and the resultant spinal loads are evaluated using our finite element model of human spine. We have used the methods proposed in this application extensively for evaluation of [bulk] lower back MB and spinal loads in asymptomatic individuals. This project will demonstrate the sensitivity of our measures for capturing abnormalities in lower back MB and spinal loads in patients with non-specific LBP by completing the following two aims to achieve our objective [*given the feasibility nature of this project and lack of adequate power, no specific hypothesis has been provided*]:

Aim-1: Feasibility of distinguishing potential differences in lower back MB between veterans with different LBP experiences. We will characterize lower back MB in three gender-balanced groups of veterans between 20 and 70 years old. These will include veterans with 1) *chronic LBP and a Roland-Morris Disability Questionnaire (RMDQ) score of >12 (n=18)*, 2) *chronic LBP and RMDQ score of ≤12 (n=18)*, 3) *no recent history of LBP and currently asymptomatic (n=18, serving as control group)*. Participants will be recruited from the population served by the Lexington, KY, VA Medical Center. We will determine passive stiffness of the lower back and its relaxation along with its active intrinsic and reflexive mechanical properties, using our sudden perturbation and stress-relaxations tests. Given the reported differences in trunk neuromuscular behavior and lumbo-pelvic coordination, we expect to see differences in our measures between patient groups targeted for this project.

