5.0 Study Procedures

5.1 Study Design

- **Study Design:** Describe experimental design of the study. Include sequential and/or parallel phases of the study, including durations, and explain which interventions are standard of care and which procedures are being done for research purposes.

This is a cross-sectional, observational study to investigate differences in **1**) active and passive aspects of lower back MB and **2**) spinal loads experienced during simulated daily activities between three veteran groups. Each participants will complete one data collection session during which they will complete a number of experiments and surveys.

- **Risk vs Benefit:** Include a description of how anticipated risk will be minimized and include an analysis of risk vs. potential benefit.

The potential risks of this study will be outlined in the informed consent document, and discussed with participants during the screening meeting. While the risk associated with the tasks performed during biomechanical assessment is no more than the risk experienced during daily life, some participants may experience muscle and/or joint soreness associated with the tests that are self-limiting and last a few minutes to a few hours. Mild discomfort may also occur during EMG preparation consisting of mild skin rubbing (with alcohol), possible shaving (with electric clippers), and the removal of adhesive tape holding the electrodes after test completion. The PI have run similar experiments with well over 100 healthy participants and 30 patients with LBP without any adverse incidents. Also, no injuries have been reported from similar measurements in the literature. Participants may feel unpleasant or uncomfortable answering some questions on the self-reported questionnaires. We will ensure participants that their answers are confidential and also inform them that they may choose not to answer any question.

Data security protections: To protect confidentiality, data on paper will be kept in locked filing cabinets and will be identifiable only by unique study ID numbers. Identifying participant information will be kept separate from other study-related materials.

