LBP is a significant health problem and is strongly associated with opioid use among veterans.³⁻⁶ Despite decades of intensive research efforts, LBP persistence, recurrence, and transition from the acute to chronic stage is not managed effectively for majority of patients.¹⁴⁻¹⁷ This clinical challenge arises, in part, because of the inability to determine the etiology of symptom (i.e., patients with non-specific LBP). The objective of this feasibility project is to verify the sensitivity of our biomechanical outcome measures for capturing potential differences in lower back mechanics between veterans with different LBP experiences. Successful completion of this project will warrant conduct of larger projects (i.e., using merit grant mechanism) to verify the role of lower back biomechanical abnormalities in LBP presentation. Given technological advances that have made biomechanical assessment more accessible, screening patients with non-specific LBP for biomechanical abnormalities can help reduce the possibility of symptom persistence and relapse due to excessive force and deformation experienced in spinal tissues. Improvement in clinical outcomes of treatment for non-specific LBP will diminish

reliance on opioids for the symptom management of particularly veterans with chronic LBP.

- **Patient Population:** Provide description of the study population (delineate all categories of subjects – patients, providers, family members, employees, etc.). Include anticipated enrollment numbers. How many participants.samples per group studies? Justify the sample size to obtain power for statistical analysis.

We will conduct a cross-sectional study involving three groups of research participants with and without LBP:

Group-1: Veterans with chronic, non-specific LBP and a Roland-Morris Disability Questionnaire (RMDQ) score of >12 (gender-balanced, n1=18)

Group-2: Veterans with chronic, non-specific LBP and a RMDQ score of ≤12 (gender-balanced, n2=18)]

Group-3: Asymptomatic veterans with no recent history of LBP (gender-balanced, n3=18)

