5.2 Recruitment Methods

- State how many subjects will be needed.
- Describe when, where, how and by whom potential subjects will be identified and recruited.
- Describe materials that will be used to recruit subjects, e.g., advertisements. Include materials as an appendix or separate attachment.

- Describe any payments to subjects, including the amount, timing (at the end of the study or pro-rated for partial study participation), method (e.g., cash, check, gift card), and whether subjects will experience a delay in receiving the payment.

We will recruit 54 gender-balanced veterans in the following three groups: 1) with chronic, non-specific LBP and a Roland-Morris Disability Questionnaire (RMDQ) score of >12 (n=18), 2) with chronic, non-specific LBP and a RMDQ score of ≤12 (n=18), 3) asymptomatic and no a recent history of non-specific LBP (n=18; serving as control group)

Participants will primarily be recruited from veteran populations receiving treatments at the Lexington VA Medical Center in Lexington, KY. This center has two facilities and several community-based clinics in the surrounding areas, and serves a population of more than 92,000 veterans. Veteran population in our local communities who do not receive care at the Lexington VA Medical Center will also be recruited. [name] (Co-I) from the Department of Physical Medicine and Rehabilitation, with assistance from [name] (Clinical Research Assistant), will lead our patient recruitment efforts.

Recruitment will be done between months 6 and 18 of the project period. During this period, PI and Co-I will meet providers that see patients with LBP to seek their assistance in identification of patients with LBP. This will include, but not limited to, primary care physicians, physical therapist, chiropractors, acupuncturists, and etc., to inform them about the study and target patient population. These providers will be asked to inform their potentially eligible patients about our study and give them our IRB approved recruitment flyer. In addition to posting flyers in these clinics, we will have one of our research staff to be present in select days to provide more information to the interested patients. We will also distribute our study flyers to local institutions that serve Veterans. The distribution of study flyers will also include the use of listservs that will be sent to Veterans who are studying at the University of Kentucky.

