5.6 Statistical Analysis

- What statistical test will be done?
- Provide sample size determination and analysis (include anticipated rate of screen failures, study discontinuations, lost to follow-up etc.).
- Describe how, where and by whom the data will be analyzed.

For each measure (i.e., reflexive latency, intrinsic stiffness, reflexive force, passive stiffness, and stress relaxation from Aim 1, along with the spinal load, SL , from Aim 2), we will run a univariate analysis of variance to verify potential differences between study groups (i.e., independent factor: participant group with five levels). A significant ANOVA will be followed with post-hoc pairwise comparison using Bonferroni's procedures. Prior to these analyses, parametric assumptions will be evaluated. As needed, data transformations will be used, or a non-parametric approach will be employed.

The statistical analyses will be led by the PI will be overseen by [name]

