5.8 Expected Results

- Based on literature and hypothesis, what can be expected?
- Alternative Hypothesis if main hypothesis is not confirmed.

This is a feasibility project and doesn't involve a specific hypothesis (per SPiRE mechanism guidelines). The followings are, however, our expected findings: Given the reported differences in physical performance between individuals with and without LBP, we expect differences in spinal loads experienced during daily activity between these groups. Considering the high rate of LBP recurrence, we specifically expect those with LBP (or a recent history LBP) to experience larger spinal loads. Furthermore, we expect differences in lower back MB between veterans with chronic and non-chronic LBP. These differences will support future longitudinal research to verify whether they are developed during transition to chronic LBP. Therefore,

successful completion of this feasibility project will pave the way for future studies (merit grant applications) that will verify the role of abnormalities in lower back MB and spinal loads in the clinical presentation of LBP. Such an understanding has the potential to help the affected veterans, particularly those with disabling non-specific LBP.

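### Section 5.6 gives the ANOVA group factor five levels, but the study has three groups; section 5.8 also states expectations about LBP categories that are not enrolled

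*Combined protocol and SAP*

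**What the plan says.** Section 5.6 applies a univariate ANOVA to six measures: reflex latency, intrinsic stiffness, reflexive force, passive stiffness and stress relaxation from Aim 1, and the spinal-load summary from Aim 2. The model is given as "independent factor: participant group with five levels". A significant result leads to Bonferroni-adjusted pairwise comparisons. A transformation or a non-parametric approach is allowed if assumptions fail, but no other number of groups is mentioned.

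The design sections describe something else. Section 5.1 sets out a comparison of "spinal loads experienced during simulated daily activities between three veteran groups", and under Patient Population says "We will conduct a cross-sectional study involving three groups of research participants with and without LBP". Section 5.2 says "We will recruit 54 gender-balanced veterans in the following three groups". The abstract and Aim 1 in section 3.0 list the same three groups of 18, and the eligibility table in section 5.4 has three group columns.

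Section 5.8 sets out expected findings. On spinal loads, "we specifically expect those with LBP (or a recent history LBP) to experience larger spinal loads". On mechanical behavior (MB), "we expect differences in lower back MB between veterans with chronic and non-chronic LBP". It adds that the MB differences will "support future longitudinal research to verify whether they are developed during transition to chronic LBP".

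**The concern.** There are two separate mismatches.

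The first is in the operative analysis sentence. The number of levels determines the ANOVA degrees of freedom and the number of pairs to which the Bonferroni adjustment applies. As written, that sentence does not describe this study, and nothing in section 5.6 lets the reader see which number is right.

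The second concerns what the study can deliver. Its stated purpose is to supply effect sizes for later grant applications, so the contrasts it can estimate should be described correctly. An expectation about chronic versus non-chronic LBP, offered as support for longitudinal work on transition to chronic pain, needs participants with non-chronic LBP. If none are enrolled, the study cannot provide that support.

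**Working it through.** **Number of groups**

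Inputs: 18 per group and three groups (section 5.1, Patient Population); total 54 (section 5.2); five levels (section 5.6).

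- Three groups: 3 × 18 = 54, which reproduces the stated total.
- Five groups of 18: 5 × 18 = 90, which does not.
- Five equal groups within 54: 54 / 5 = 10.8, not a whole number.

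No section examined defines a fourth or fifth group. The only other five that might explain the text is the upper limit of the sum in the Aim 2 spinal-load formula (section 5.5). That counts activities, which are combined into one value per participant before the ANOVA. Section 5.6 says explicitly that its factor is participant group.

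**What the number of levels determines**

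With k levels and N = 54 complete cases, the degrees of freedom are k − 1 and N − k, and the number of pairs is k(k − 1)/2.

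| | Three levels | Five levels, taken literally |
|---|---|---|
| Degrees of freedom | 2, 51 | 4, 49 |
| Critical F at 0.05 | 3.18 | 2.56 |
| Pairs per measure | 3 | 10 |
| Bonferroni threshold per pair | 0.05/3 = 0.0167 | 0.05/10 = 0.005 |

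The right-hand column cannot arise from the data, because there are only three groups to fit. The one route by which the error could affect a result is if someone set the Bonferroni divisor by hand from the text. For that case only, the difference detectable with 80% power was computed from the noncentral t distribution (18 per group, two-sided, pooled variance on 51 df):

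- threshold 0.0167: critical t 2.476, detectable difference 1.11 SD;
- threshold 0.005: critical t 2.934, detectable difference 1.27 SD.

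Using the second threshold would mean counting 10 − 3 = 7 comparisons that cannot be made, so this is not a predicted loss of power.

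**Expectations in section 5.8 against eligibility in section 5.4**

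| Category named in 5.8 | Eligible group in 5.4 | Planned participants |
|---|---|---|
| Chronic LBP | Groups 1 and 2 | 36 (2 × 18) |
| Non-chronic LBP | None; both LBP groups must be chronic | 0 of 54 |
| Recent history without current LBP | None; Group 3 must have no recent history | 0 of 54 |
| No LBP | Group 3 | 18 |

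The brief screening list in section 5.4 treats a recent history and no recent history as different answers, so Group 3 cannot be read as including the former. The comparison of LBP with no LBP, which section 5.8 also expects for spinal loads, can be made.

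**The case against.** The strongest reply is that this is a one-word slip with only one sensible reading. Software fits the levels present in the data. The test, the adjustment, the sample size and the eligibility rules all stay the same. Section 5.6 says the ANOVA compares the study groups, and those are defined consistently wherever they are defined. Section 5.8 is narrative: it opens by saying there is no specific hypothesis, and its expectations feed no test in section 5.6. The recent-history phrase is a parenthetical alternative, so the sentence works without it. The figures of 90 participants and 1.27 SD describe a study that will not be run.

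Much of this stands. No bias or invalid result follows, and the conditional figures carry no weight in judging the size of the problem. The chronic versus non-chronic clause is the more substantial part of the section 5.8 point.

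Two things remain. The wrong number is in the only statement of the model, not in background text. And the chronic versus non-chronic expectation is more than loose wording, because the following sentence relies on it as evidence for future research.

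**Conclusion.** Both points hold. Section 5.6 states five levels for a design with three groups (54 = 3 × 18), and this applies to all six measures. Section 5.8 contains one expectation (chronic versus non-chronic LBP) and part of another (recent history of LBP) for which no participants are planned.

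The practical effect is limited, since the analysis of the collected data will have three levels and the study declares no formal hypothesis and inadequate power (section 3.0). It should still be fixed, because the analysis section and the expected findings should describe the study that is planned and the correction is nearly free.

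The 2 and 51 degrees of freedom assume complete data on all 54 participants. The personnel and resources sections (1.0 and 4.0) were not in the text examined; the conclusion assumes that they define no further groups. The documents do not say how the five arose, and nothing here depends on it.

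**What to change.** 1. In section 5.6, replace five levels with three and name them: chronic LBP with RMDQ >12, chronic LBP with RMDQ ≤12, and asymptomatic. This alone removes the contradiction. Optionally, state that there are three pairwise comparisons per measure and name the Bonferroni family (0.05/3 = 0.0167 if applied within each measure).
2. In section 5.8, restate the expectations as contrasts among enrolled groups: Groups 1 and 2 against Group 3 for LBP versus no LBP, and Group 1 against Group 2 for higher versus lower disability. Remove the chronic versus non-chronic expectation and the recent-history parenthesis, or mark them as outside this study. The sentence about supporting longitudinal research should then refer only to contrasts that can be estimated.
3. Optionally, align the Aim 2 rationale in section 3.0, which mentions non-chronic and recent-history LBP as background but specifies no contrast with them.

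The cost is a few changes of wording. No new data, no change in sample size and no change of method are needed.

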Sample size justification: The purpose of this SPiRE project is to generate the required data for effect size calculation of future merit grants. In the absence of preliminary data from veterans with LBP, we calculated a sample size using effect sizes estimated from our earlier investigations of back-healthy individuals as well as reports of relevant measures in the literature. Based on our earlier studies of asymptomatic individuals,^{56, 57, 66} a sample size of 10 would have a power of >80% for detection of significant (p = 0.05) differences in the proposed measures of lower back MB following acute exposure to awkward working posture. Further, using results in the literature,⁶⁷⁻⁶⁹ a sample size (i.e., sum of two groups) of 18 was estimated to detect reported significant effect sizes between individuals with and without LBP with 80% power. Therefore, a sample size of 18 for each group is selected to facilitate sample size calculation and power analyses for our future merit grant applications while maximizing our chances of discovering potential differences in lower back MB and spinal loads between groups.

- **Vulnerable Populations:** As applicable, provide information on any added protections for vulnerable populations.

Not Applicable

- **Data and Specimen Banking:** If applicable include information on data and specimen banking.

Not Applicable

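### Section 5.6 makes pairwise comparisons conditional on a significant ANOVA and names no effect estimate or confidence interval, although data for effect size calculation are a stated purpose

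*Combined protocol and SAP*

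**What the plan says.** Section 5.6 plans a one-way ANOVA for each of six measures: reflex latency, intrinsic stiffness, reflexive force, passive stiffness, stress relaxation and the spinal load SL. Its only rule for pairs of groups is "A significant ANOVA will be followed with post-hoc pairwise comparison using" Bonferroni's procedures. If assumptions fail, "data transformations will be used, or a non-parametric approach will be employed", with no estimator named for either route. The factor is described as "independent factor: participant group with five levels", while sections 3.0, 5.1 and 5.2 all define three groups of 18.

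The sample size justification in section 5.1 states: "The purpose of this SPiRE project is to generate the required data for effect size calculation of future merit grants". It adds that "a sample size of 18 for each group is selected to facilitate sample size calculation and power analyses for our future merit grant applications", and the same sentence gives a second aim, to have the best chance of finding group differences. Section 3.0 says that "given the feasibility nature of this project and lack of adequate power, no specific hypothesis has been provided".

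The data-analysis paragraphs in section 5.5 define how each participant's outcome is derived. They do not say how differences between groups will be estimated.

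**The concern.** A study that claims no hypothesis and not enough power, and that is meant to inform later sample sizes, needs estimates with their uncertainty for every contrast of interest. As written, contrasts are planned only where the ANOVA is significant. This has two consequences.

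- A measure whose ANOVA is not significant ends with no planned contrast. With low power this could happen often.
- Contrasts that do follow a significant ANOVA are a selected set. When power is low they overstate the true difference on average, so a later study sized on them alone could be too small.

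The open fallback to transformation or rank methods adds a smaller difficulty: the scale and the estimator could be chosen after the data are seen.

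**Working it through.** **Inputs from the documents.** Three groups of 18 (sections 3.0, 5.1, 5.2), six measures (5.6), p = 0.05 (5.1). Residual df = 54 - 3 = 51.

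**The plan's own figure.** Section 5.1 says that "a sample size (i.e., sum of two groups) of 18 was estimated to detect reported significant effect sizes" between people with and without LBP, with 80% power. The effect size, sidedness and split are not stated, so the 18 can only be back-solved. With 9 vs 9 and a two-sided t-test at 0.05 it implies d = 1.41. One-sided it implies 1.23, and with a 6 vs 12 split, two-sided, 1.49.

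**Assumed true effects.** Group 1 minus Group 3 of 0.5, 0.8 or 1.41 SD, with Group 2 either midway or equal to Group 1. The first two are assumptions. The third is the back-solved value.

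**Probability of a significant ANOVA.** The noncentrality is λ = 18 × Σ(δᵢ - mean δ)², and the critical value of F on (2, 51) df is 3.18. For (0.5, 0.25, 0), λ = 18 × 0.125 = 2.25. For (0.5, 0.5, 0), λ = 18 × 0.1667 = 3.00. The noncentral F probabilities are 0.237 and 0.305.

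**Size of the estimate and coverage.** Simulation with 1,000,000 runs per row, normal data, pooled SD on 51 df, Hedges correction 1 - 3/(4 × 51 - 1) = 0.985. Coverage is that of the 95% t-interval for the raw Group 1 minus Group 3 difference, among studies with a significant ANOVA.

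| True effect, Group 2 position | λ | ANOVA significant | Mean g if significant | Mean g, all studies | Coverage if significant |
|---|---|---|---|---|---|
| 0.5, midway | 2.25 | 24% | 0.90 | 0.50 | 89% |
| 0.5, equal to Group 1 | 3.00 | 31% | 0.82 | 0.50 | 91% |
| 0.8, midway | 5.76 | 54% | 1.04 | 0.80 | 95% |
| 0.8, equal to Group 1 | 7.68 | 67% | 0.95 | 0.80 | 96% |
| 1.41, midway | 17.8 | 96% | 1.43 | 1.41 | not reduced |
| 1.41, equal to Group 1 | 23.8 | 99% | 1.41 | 1.41 | not reduced |

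Without selection, coverage is 95% in every row. In the fifth row the bias is 1.434/1.407 - 1 = 1.9%; in the sixth it is 1.413/1.407 - 1 = 0.4%.

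**Precision without selection.** For a standardised difference, the 95% CI half-width at 18 per group is about 0.65 SD at d = 0 and 0.67-0.68 SD at d = 0.8. An observed 0.5 has a noncentral-t interval of -0.16 to 1.16 on 51 df. The SD of the unselected g is 0.34 at a true 0.5.

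**Bonferroni divisor.** Three groups give 3 × 2/2 = 3 pairs, or 0.05/3 = 0.0167 each. Five levels would give 5 × 4/2 = 10 pairs, or 0.005 each.

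**The case against.** The strongest reply is that this is an omission and not a rule against estimation. Section 5.6 answers a template prompt asking which test will be done, and nothing limits reporting to p-values. The ANOVA is run for all six measures whatever its result, and it supplies group means and a residual mean square, which is the squared pooled SD. Those are data from which effect sizes can be calculated. Bonferroni procedures can also give intervals. All of this stands.

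The study also has a second purpose, to show that the measures can distinguish the groups, and ANOVA with post-hoc comparisons serves that directly. This stands too.

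A reader might infer that the study will produce only p-values and so cannot deliver what it was set up for. The documents do not support that, for the reasons just given. A reader might also infer that future planning will be biased. That needs two further conditions: true effects that are small to moderate, and planners who use only contrasts that followed a significant ANOVA. No section states either. At the one effect that can be back-solved from section 5.1, the bias nearly vanishes. Loss of coverage is not general either: it appears at 0.5 SD and not at 0.8 SD.

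What the reply does not remove is that the contrasts, scale, estimator and intervals needed for effect size calculation are left unplanned, and that the one rule given for pairs is conditional on significance.

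**Conclusion.** The point holds as a gap between a stated purpose and the written analysis, and it should be corrected. A measure with a non-significant ANOVA has no planned contrast, and no effect estimate or interval is specified for any pair.

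The upward bias is a conditional risk. For Group 1 vs Group 3 it is about 0.32-0.40 SD at an assumed true effect of 0.5 SD (0.82 - 0.50 to 0.90 - 0.50), about 0.15-0.24 SD at 0.8, and at most about 2% at 1.41. These figures rest on normal data, equal variances, full enrolment of 18 per group and the assumed positions of Group 2. They apply only if contrasts selected by the ANOVA are the ones carried forward.

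The factor levels in 5.6 contradict the three groups defined elsewhere and leave the Bonferroni divisor at 3 or 10.

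**What to change.** Add to section 5.6:

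> For all six measures and all three pairs of groups, the difference, pooled SD and Hedges g with 95% CI will be reported whatever the ANOVA p-value. If data are transformed, these will be given on the transformed scale. If the non-parametric route is used, a rank-based effect (Hodges-Lehmann shift and probability of superiority) with 95% CI will be given instead. These estimates are descriptive. Planning of future studies will use them together with their intervals, not the point estimates alone.

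Keep the ANOVA and the Bonferroni comparisons for any claim of significance. Change the number of factor levels to three, so that the divisor is 3 pairs.

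The cost is a few sentences and one extra table per measure. Enrolment, procedures and tests are unchanged. The downside is 6 × 3 = 18 descriptive estimates with wide intervals (about ±0.65-0.68 SD for d up to 0.8) and no multiplicity control. The change removes the selection but not the imprecision of 18 per group, so the intervals matter as much as the estimates.
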